### Demographic and Baseline Clinical Characteristics:

- Age, as determined via electronic medical record (EMR)
- Diagnosis and diagnostic stage, as determined via EMR
- Diagnosis Date, as determined via EMR
- Body mass index, as determined by height and weight in EMR
- Comorbid chronic conditions (hypertension, diabetes, COPD), as determined via EMR
- Race/ethnicity, as determined via EMR

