## **4.0 Study Endpoints\***

### Primary Study Endpoints:

- Total number of missed fractions, determined via EMR
- A break in cancer treatment, defined as missing  $\geq 3$  fractions due to patient condition, determined via EMR
- ER visits, as determined via EMR
- Inpatient and outpatient hospital encounters, as determined via EMR
- Hospital readmission for the same presenting issue, as determined via EMR
- Hospital length of stay (if hospitalized), as determined via EMR
- Cancer treatment adherence, determined via EMR
- Medications for cancer treatment symptom management, determined via EMR
- Cancer treatment-related side effects, determined via EMR
- Patient-rated pain measured by visual analog scale, as determined via EMR
- Cancer treatment tolerance, measured by the Eastern Cooperative Oncology Group (ECOG) Performance Status score, as determined via EMR
- Quality of Life, as measured by the McGill Quality of Life Measure, administered in-person at weeks 1 and 12  
[\(http://www.npcrc.org/files/news/mcgill\\_quality\\_of\\_life.pdf\)](http://www.npcrc.org/files/news/mcgill_quality_of_life.pdf)

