### Data Analysis Plan:

Data will be analyzed using IBM SPSS Statistics version 25.0. Continuous variables will be described using mean, median, standard deviation, and range. Nominal variables will be described using frequency and percentage.

Baseline demographic and clinical characteristics will be compared between treatment and control groups to establish equivalence; any statistically significant differences between study groups will be controlled statistically. Continuous endpoints will be tested for normality using Shapiro-Wilk tests. Differences between study groups on continuous endpoints will be evaluated using independent samples *t*-tests for normally distributed endpoints and Mann-Whitney *U* tests for non-normally distributed endpoints. Nominal endpoints will be compared between groups using chi-square tests. Alpha will be set to .05, two-tailed for all tests.

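### No pre-randomisation value of the EMR outcomes is listed at baseline and no outcome test carries a baseline term, so precision is given away, by an amount the documents do not let us fix

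*Combined protocol and SAP*

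**What the plan says.** Section 4.0 has a list headed "Demographic and Baseline Clinical Characteristics". It starts with age, covers diagnosis, stage, diagnosis date and body mass index, and ends with "Race/ethnicity, as determined via EMR". The item nearest to prior health status is "Comorbid chronic conditions (hypertension, diabetes, COPD), as determined via EMR".

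The primary endpoints in the same section include "Cancer treatment tolerance, measured by the Eastern Cooperative Oncology Group (ECOG) Performance Status score, as determined via EMR" and "Medications for cancer treatment symptom management, determined via EMR". ER visits, inpatient and outpatient encounters, and pain on a visual analogue scale are also primary endpoints from the EMR. None has a baseline time point. Quality of life is the only outcome with a planned early measurement, at weeks 1 and 12.

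The Data Analysis Plan in section 17.0 states: "Differences between study groups on continuous endpoints will be evaluated using independent samples" t-tests, or Mann-Whitney tests when normality is rejected. Nominal endpoints get chi-square tests. The only adjustment rule covers baseline characteristics that differ significantly between the groups. No section plans ANCOVA, a change score or a baseline-adjusted count model.

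**The concern.** A patient's earlier value of an outcome is usually a natural covariate for that outcome. Patients may enter up to 12 weeks after diagnosis (section 10.0), so some may already have encounters, symptom drugs or a recorded ECOG or pain score. Omitting these values leaves between-patient variation in the error term that a covariate could remove.

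The adjustment rule does not fill the gap. It cannot act on a variable that is not on the list. For one that is, correct randomisation triggers it only about 5% of the time at the 0.05 level, and the size of the imbalance says little about how well the variable predicts outcome. Quality of life shows that the list is not the only cause: an early score is planned, yet the analysis does not use it. The remedy therefore needs both the extra variables and a prespecified model.

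**Working it through.** **Inputs.** 70 patients, 35 per arm, 80% power for a medium effect on missed fractions (section 12.0); two-sided alpha 0.05 (section 17.0). Assumed, because the documents give neither: standardised difference d = 0.5 as the usual reading of medium, and a correlation r between baseline and outcome from 0.2 to 0.6.

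**1. The plan's own figure.** The noncentrality is d × sqrt(n/2) = 0.5 × sqrt(35/2) = 2.09.
- Normal approximation: Φ(2.09 − 1.96) = 55%.
- Noncentral t: 54%.

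The stated 80% does not reproduce. It would need 64 per arm at d = 0.5, or d of about 0.68 with 35 per arm. A one-sided test gives 66–67%, and reading medium as a correlation of 0.3 (d = 0.63) gives 74%. This is a separate matter; 54% serves here only as the unadjusted reference.

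**2. Chance imbalance.** The SD of the chance difference between arms in a baseline variable is sqrt(2/35) = 0.24 SD. It reaches the outcome multiplied by r:
- r = 0.2: 0.2 × 0.24 = 0.05 SD
- r = 0.3: 0.07 SD
- r = 0.5: 0.12 SD
- r = 0.6: 0.14 SD

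The unadjusted standard error already includes this variation.

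**3. Gain from adjustment.** Residual variance is multiplied by 1 − r². Effective N is 70/(1 − r²). Power is taken from the noncentral t at d/sqrt(1 − r²) with 35 per arm. The detectable difference is 0.679 × sqrt(1 − r²).

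| r | 1 − r² | Effective N | Power at d = 0.5 | d detectable with 80% power |
|---|---|---|---|---|
| 0 | 1.00 | 70 | 54% | 0.68 |
| 0.2 | 0.96 | 73 | 56% | 0.67 |
| 0.3 | 0.91 | 77 | 58% | 0.65 |
| 0.5 | 0.75 | 93 | 66% | 0.59 |
| 0.6 | 0.64 | 109 | 73% | 0.54 |

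A correlation of about 0.68 would be needed for 80% power at d = 0.5.

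**4. Where the table applies.** The formula is for a continuous, roughly normal outcome. It fits pain and quality of life best. ECOG is a short ordinal score, ER visits are likely to be sparse counts, and drugs may be counts or yes/no. For those the table shows direction, not size.

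**The case against.** The strongest reply is that randomisation already protects the comparison, so this is a refinement whose benefit is unknown. Much of that stands. No correlation is given, and the patients have stage 0 to 2 disease and physician clearance for exercise. Entry ECOG and prior ER use may therefore vary little, and at r = 0.2 the gain is two points of power. Encounters before entry may largely reflect diagnostic work-up and predict later use poorly. The value d = 0.5 comes from the sample size statement for missed fractions, which would usually have no pre-randomisation counterpart, so the sizing endpoint gains nothing.

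Four stronger readings are tempting, and the documents support none of them:

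- **That the comparison is biased.** It is not. Chance imbalance is part of the stated error, and it passes through scaled by r, not in full.
- **That a drug started before entry will be counted as an outcome.** Section 4.0 gives no counting window or rule for medications. It is silent, and silence does not establish this.
- **That the imbalance can never be seen or removed.** Sections 9.0 and 17.0 have the EMR data abstracted by report once all patients have finished, so a look-back could recover earlier values where they were recorded.
- **That all these outcomes are final values compared raw.** Section 2.0 assesses H1 over 3 months, so ER visits and hospital encounters are counts over follow-up, for which prior use is a covariate.

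What the reply does not remove is that the covariates probably exist in the same record system, the plan does not use them, and its adjustment rule selects covariates on the wrong criterion.

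**Conclusion.** The point holds as one about precision. The baseline list contains no earlier value of ECOG, pain, ER visits, hospital encounters or symptom drugs, and no outcome analysis, including that of quality of life, has a prespecified baseline term.

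The size is uncertain. Under normal theory with d = 0.5 and 35 per arm, the gain runs from 2 points of power (r = 0.2) to 19 (r = 0.6, 73% against 54%). The low end is plausible for ECOG and ER use; no correlation in the documents supports the high end. The gain does not extend to missed fractions, and it should not be read as an answer to the section 12.0 power statement. The change is worth making because it is cheap and the trial has little precision to spare.

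**What to change.** **Section 4.0, baseline list.** Add, from the same EMR report:
- the last ECOG score and last pain score before randomisation;
- ER visits and hospital encounters in a fixed, stated window before randomisation;
- symptom-management drugs active at randomisation.

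**Section 17.0, Data Analysis Plan.** Replace adjustment after a significant difference with prespecified covariates. Each value enters the model for its own endpoint whatever its baseline p-value, and the choice is fixed before outcome data are examined:
- ANCOVA for pain and quality of life, using the week 1 quality-of-life score only if it is taken before exercise begins, which the protocol should state;
- a count model for ER visits and hospital encounters;
- an ordinal model for ECOG;
- for symptom drugs, a model that adjusts for use at randomisation. Counting only new starts would redefine a primary endpoint and would hide an existing drug being stopped or reduced.

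**Cost.** A longer look-back in an EMR report that is already planned, and a few lines of analysis text. No extra visit is needed for the EMR items. Some patients will lack a pre-randomisation ECOG or pain entry; a missing-indicator category keeps them in the analysis. The documents do not say how complete these entries are.

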## 3.0 Background\*

In 2018, it was estimated that there were 1.7 million new cancer diagnoses in the U.S. For all types of cancer, mortality rates are on the decline, and patients are living longer with the chronic and late effects of treatment. This often results in costly hospital readmissions and emergency department (ED) visits, leading to increased costs, lowered health outcomes, and lengthened stays for patients.

Several meta-analyses report that exercise interventions are beneficial for patients undergoing cancer treatment, in that they reduce symptom severity and improve cancer-related fatigue, cardiac function, muscle weakness, and overall quality of life. Yet, it still remains that less than 5% of patients are ever referred to an exercise oncology program during treatment. Therefore, economic evaluations of exercise oncology are warranted, in attempt to evaluate the integration of exercise oncology as a standard part of clinical practice.

Maple Tree Cancer Alliance has developed an oncology exercise program, which results in improved health outcomes, and also cost-saving for facilities and payers. Our retrospective data demonstrated that individualized exercise during cancer treatment significantly reduced ED visits, 30-day readmissions, and length of hospital stays resulting in a payer benefit of \$3,000/patient over the first 6 months of enrollment into the Maple Tree Exercise Oncology program^2. As a follow up to this research, the purpose of the present study is to prospectively analyze the cost savings of an individualized exercise oncology program when under a rigorous, randomized, controlled design. We hypothesize that

**PROTOCOL TITLE:** Randomized, Controlled Trial of an Individualized Exercise Oncology Program for Newly Diagnosed Breast Cancer Patients

individualized exercise training during cancer treatment will improve treatment outcome, lending to a decrease in healthcare-related expenditure.

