## 6.0 Procedures Involved\*

The study design is an open-label, randomized, controlled, parallel-group trial. Women age 30-80 with a recent diagnosis of stage 0, 1 or 2 breast cancer who meet inclusion and exclusion criteria will be invited to participate. As is typical and customary, a diagnosis within the last 12 weeks will be considered a recent diagnosis. Upon study enrollment and informed consent, patients will be randomly assigned to the Exercise Group or the Control Group. Random assignment will be conducted in blocks of 10 to ensure equal groups (See Appendix A). Participants will be enrolled in the study for 12 weeks.

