## **10.0 Inclusion and Exclusion Criteria\***

Patients will be selected according to the Consolidated Standard of Reporting Trials criteria. Criteria not determined via EMR are determined via the form in Appendix B. Inclusion criteria are:

- Female; determined from electronic medical record
- Initial stage 0, 1 or 2 breast cancer diagnosis within the past 12 weeks determined from electronic medical record
- Age 30-80; determined from electronic medical record
- Physician clearance to participate in exercise

Exclusion criteria are:

- Participation in supervised physical exercise within 6 months prior to study enrollment
- Currently pregnant or planning to become pregnant
- Non-English speaking
- Unable to make own medical decisions and/or to follow verbal instructions

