## 12.0 Local Number of Subjects

A total of 70 subjects will be enrolled (35 in each study group). This sample size provides 80% power to detect a medium effect size in number of missed treatment fractions between study groups. Only subjects who meet eligibility criteria will be enrolled.

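### Planned cancer treatment is neither a listed baseline variable nor a pre-specified covariate, which costs precision and leaves a chance treatment imbalance unadjusted under the plan as written

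*Combined protocol and SAP*

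**What the plan says.** Section 4.0 of the combined protocol and SAP lists the baseline characteristics. The clinical items are "Diagnosis and diagnostic stage, as determined via EMR", "Diagnosis Date, as determined via EMR", body mass index and "Comorbid chronic conditions (hypertension, diabetes, COPD), as determined via EMR"; the others are age and race/ethnicity. No item records the treatment planned or its start date. In the same section, treatment appears only on the outcome side: missed fractions, treatment breaks, treatment adherence, symptom medication and side effects.

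Section 10.0 defines the disease criterion as "Initial stage 0, 1 or 2 breast cancer diagnosis within the past 12 weeks determined from electronic medical record". It neither requires nor excludes any type or phase of treatment, and section 24.0 leaves treatment decisions outside the study.

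Section 17.0 (Data Analysis Plan) compares the arms by t-test, Mann-Whitney U or chi-square test. On covariates it says only that "any statistically significant differences between study groups will be controlled statistically", referring to the baseline comparison.

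The hypothesis in section 3.0 is that "individualized exercise training during cancer treatment will improve treatment outcome, lending to a decrease in healthcare-related expenditure".

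**The concern.** The trial asks what exercise does while patients are being treated, and section 3.0 itself links ED visits and readmissions to the effects of treatment. Yet under section 10.0 one participant may spend her 12 weeks on chemotherapy, another recovering from surgery and a third on little active treatment. If treatment strongly influences ER visits, encounters, side effects, symptom medication and pain, two things follow. Variation due to treatment stays in the error term, so the comparison is less precise than it could be. And if one arm happens to receive more chemotherapy patients, the estimate in that trial is shifted, with no planned step to adjust for it. Stage and diagnosis date are partial stand-ins: they do not identify who has chemotherapy in the 12-week window.

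The point concerns the utilisation, side-effect, symptom-medication and pain endpoints. It is not about how missed fractions are defined or powered.

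**Working it through.** The plan gives no figure on this point to reproduce. The power statement in section 12.0 concerns missed fractions and does not enter here.

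**Inputs from the documents.** "A total of 70 subjects will be enrolled (35 in each study group"), so n = 35 per arm. Alpha is 0.05 two-sided (section 17.0).

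**Assumed inputs, because the documents give none.** Share of patients on chemotherapy p = 40% (range 30% to 50%). Mean ER visits over 12 weeks: 0.6 with chemotherapy and 0.1 without (range 0.4/0.1 to 1.0/0.2). Visits are Poisson within each treatment group.

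**1. How often the arms differ.** Take the chemotherapy counts in the two arms as independent Binomial(35, p). The exact probability of a difference of 5 or more patients is 24.0% at p = 30%, 27.2% at 40% and 28.2% at 50%.

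**2. Shift from a 5-patient gap with no exercise effect.** Shift = (5/35) × (rate with chemotherapy − rate without). Overall mean = 0.4 × rate with + 0.6 × rate without. Variance = mean + 0.4 × 0.6 × (rate difference)². Standard error of the difference = √(2 × variance/35).

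| Rates with/without | Mean | Shift | Shift/mean | Variance | SE | Shift/SE |
|---|---|---|---|---|---|---|
| 0.4/0.1 | 0.22 | 0.043 | 19% | 0.242 | 0.117 | 0.36 |
| 0.6/0.1 | 0.30 | 0.071 | 24% | 0.360 | 0.143 | 0.50 |
| 1.0/0.2 | 0.52 | 0.114 | 22% | 0.674 | 0.196 | 0.58 |

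**3. Effect on the test in such a trial.** Simulating 12 versus 17 chemotherapy patients at 0.6/0.1, with no exercise effect and a t-test, gives a two-sided false-positive rate of 5.6%. Significance favouring the arm with fewer chemotherapy patients occurs in just over 5% of trials, against a nominal 2.5%. Averaged over all randomisations the two-sided rate is 5.0%.

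**4. Precision available from adjustment.** Share of variance due to treatment = 0.24 × (rate difference)²/variance. This is 0.24 × 0.25/0.36 = 16.7% at 0.6/0.1, 8.9% at 0.4/0.1 and 22.8% at 1.0/0.2. The standard error falls by 1 − √(1 − share): 8.7%, 4.6% and 12.1% respectively.

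**5. Would listing treatment at baseline be enough?** Not under the present rule. For 12/35 versus 17/35 the pooled share is 29/70 = 0.414, so z = (5/35)/√(0.414 × 0.586 × 2/35) = 0.143/0.118 = 1.21 and p = 0.225 (uncorrected chi-square). Even 12 versus 20 gives p = 0.055. At p = 40%, a gap of 6 or more has probability 17.9%, and 13.1 of those 17.9 points (73%) are not significant. For shares of 20% to 60% the unadjusted fraction runs from 52% to 77%.

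**The case against.** The strongest reply is that randomisation already deals with this. It does, on average: the overall type I error stays at about 5%, and a false shift of half a standard error is modest. Larger gaps do more harm but are rare; a 10-patient difference has a probability of about 2% at a 40% share. That part of the reply stands and limits the claim to precision and conditional bias.

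A reader might infer that an imbalance in treatment could be neither detected nor corrected. The documents do not support that. Section 9.0 has EMR data abstracted after follow-up, and several section 4.0 endpoints require the treatment record, so treatment could be examined later. The gap is that nothing is pre-specified, and a covariate chosen after results are seen, or based on treatment as modified after randomisation, is less credible.

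A reader might also fault the allocation because "Random assignment will be conducted in blocks of 10 to ensure equal groups" without strata. Unstratified blocks are an accepted choice with 70 patients, and the remedy here does not depend on stratifying.

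Two further limits stand. The documents contain no figure for how strongly treatment drives these outcomes, so its prognostic strength is a reasoned assumption. And the arithmetic covers ER visits only; nothing has been computed for side effects, symptom medication or pain.

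**Conclusion.** The omission is confirmed by the text: planned treatment is absent from the baseline list and from the analysis, and the significance-triggered rule would miss most relevant imbalances even if it were listed. The consequence is moderate. On the assumed 40% share and 0.6/0.1 ER rates, a gap of 5 or more patients arises in about 27% of randomisations. A gap of exactly 5 moves the ER-visit difference by 0.07 visits (24% of the mean; 19% to 24% over the rates tried), or about 0.5 standard errors (0.36 to 0.58). Adjustment would reduce the standard error by about 9% (5% to 12%). The finding that treatment is not pre-specified does not depend on these assumptions; the sizes do. The trial is not invalidated, and the change is worth making because it is cheap.

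**What to change.** In section 4.0, add to the baseline list and baseline table the treatment plan as recorded in the EMR before randomisation: surgery pending or done; chemotherapy yes, no or not yet decided; radiotherapy yes, no or not yet decided; and start dates.

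In section 17.0, pre-specify planned chemotherapy as a covariate for the utilisation, side-effect, symptom-medication and pain endpoints, whether or not it differs significantly at baseline. Keep the undecided group as its own category or, if it is rare, merge it by a rule fixed in advance.

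The t, Mann-Whitney and chi-square tests now named cannot take a covariate, so name models that can. Examples are:
- negative binomial regression, or Poisson regression with robust errors, for ER visits, encounters and symptom medications;
- logistic regression for binary endpoints, or a Mantel-Haenszel test stratified by chemotherapy where events are sparse;
- ANCOVA for pain.

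Side effects would follow the count or the binary model, according to how they are scored.

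**Cost.** A few more fields in an EMR report that is already planned, a short rewrite of section 17.0, one or two degrees of freedom per model, and regression in place of simple tests. Plans must be analysed as first recorded, even if they change later.

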## 5.0 Study Intervention/Investigational Agent

### Exercise Group

The study intervention is a supervised, individualized exercise oncology program described in previous literature and provided by Maple Tree Cancer Alliance, a non-profit organization providing exercise training to individuals with cancer (<https://www.mapletreecanceralliance.org/>). This organization was founded in 2011 and currently operates in 9 hospitals serving Ohio and Pennsylvania, offering free exercise programs and nutritional guidance to approximately 500 patients annually to help relieve side effects related to cancer treatment.

Patients in the supervised, individualized exercise oncology program (Exercise Group) will complete a 60-minute exercise session once per week for 12 weeks at Maple Tree Cancer Alliance. The exercise sessions will be individualized to the patient's needs and fitness level by a trainer with a bachelor's degree in exercise science and a national certification for exercise oncology. A patient will work with the same trainer throughout the study, who will plan the patient's individualized exercise regimen, and who will provide one-on-one supervision for the duration of each 60-minute session. Each 60-minute session will include cardiovascular, strength, and flexibility training.

Cardiovascular exercise will be performed on a treadmill. The intensity level for the aerobic exercise ranges from 30-45% of the individual's predicted VO2max, controlled by heart monitors (model S810i; Polar Electro) and lasting 30 min. Strength training will involve a full body workout, with emphasis on all major muscle groups and employing machines, free weights, and resistance tubing. Patients will complete 3 sets of 10 repetitions for each strength exercise. Flexibility training will involve static stretching of all major muscle groups for 15-20 seconds at the completion of each workout.

